Back pain is common in all age groups (1), and one systematic review highlights that disabling back pain is more prevalent in older people than in younger people (2). The clinical course of back-related disability in older adults with back pain has not been extensively studied. Two studies suggests that improvements in disability were modest the first three months, with little to no improvements on group level after three months (3, 4). It is well documented that number of comorbidities are associated with the clinical course of back-related disability in older adults, but the prognostic value of comorbidity is still highly uncertain (5-11).

Study aim:

The primary aim of this study is to examine the clinical course of back-related disability measured at baseline, 3, 6 and 12 months after a new episode of back pain. The secondary aim is to assess the prognostic value of number and severity of comorbidity at baseline for changes in back-related disability over one year of follow-up.

Study design and method

Study design

BACE-N is based on the previously published BACE study protocol from the BACE international consortium (12). The BACE-N protocol has been published (ClinicalTrials.gov Identifier: NCT04261309).

The BACE-N study is a prospective observational cohort study with a 2-year follow-up time. This study will use data from baseline, 3, 6 and 12 months of follow-up. Design of the study was made within the framework PROGnosis RESearch Strategy (PROGRESS), which is a framework for ensuring and enhancing the quality of prognostic studies (13). The primary aim is relating overall prognosis, and the secondary aim is relating confirmatory prognostic factor research (13, 14).

Study population

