The prognostic factor of interest is comorbidity measured at baseline with a modified version of the Self-administered Comorbidity Questionnaire (SCQ) (19). The original questionnaire measures 13 pre-specified comorbidities, and 2 non-specified. The item “back pain” has been removed for this study and replaced with an additional non-specified item. Thus, the count of comorbidity ranges from 0-15. The diseases listed are: Heart disease, high blood pressure, lung disease, diabetes, ulcer or stomach disease, kidney disease, liver disease, anemia or other blood disease, cancer, depression, osteoarthritis, rheumatoid arthritis and up to 3 non-specified comorbidities. The SCQ measures comorbidities on three levels: 1) Do you have the problem? 2) Do you receive treatment for it? 3) Does it limit your activities? All levels are answered on a dichotomous yes/no level, and you only answer level 2 and 3 if you have answered “yes” on level 1. An individual can receive a maximum of 3 points for each medical condition: 1 point for the presence of a comorbidity, 1 point if they receive treatment for the condition, and 1 point if the condition limits their functioning. The maximum score for the full SCQ is thus 45 points.

We plan to use SCQ part 1 comorbidity count (0-15 scale), and the full SCQ (0-45) in separate models. Previous studies have found linear relationships between comorbidity and back-related disability (7, 11), and thus we plan to treat these variables as linear. Linearity with outcome will be assessed, and deviations will be handled appropriately.

Covariates:

Covariates are presented in table 1. They are chosen based on being “established” prognostic factors in the literature, having been utilized in similar studies previously (to enhance comparability), and for being readily available and easy to measure in clinical practice.

Table 1: Covariates, measurement level and/or instrument, rationale for inclusion		
Factor	Measurement level	Rationale
Age	Continuous, minimum age ≥ 55	Standard covariate in previous studies (7, 8, 10), and in some studies reported to be associated with disability levels in older adults (4, 6, 20)
Sex	Dichotomous	Standard covariate in previous studies (7, 8, 10), and in some studies reported to be associated with disability levels in older adults (6, 20)
BMI	Measured continuous, divided into categories: <20, 20-25, 25-30, <35	Covariate in previous study (7), and found to be associated with disability in older adults (4, 21)

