According to the STRATOS initiative task force, a complete prespecifying of all aspects in model building is unrealistic in observational studies (24). Thus, the following will provide a framework for analysis and model building in this study, not a detailed recipe. Decisions regarding final choice of models will be made by the first author, the advisory statistician and the principal investigator.

Primary aim, clinical course of back-related disability:

Mixed models for repeated measures will be used to account for statistical dependencies. RMDQ is the dependent variable, and time and first contact health provider will be entered as fixed factors. The exact handling of time as a continuous or categorical variable depends on the distribution. Previous studies have found that the clinical course of a back episode is not linear over time (3, 25, 26). It is therefore reasonable to believe that time will have to be treated as a categorical variable, or by introducing a quadratic term, depending on its distribution. Choice of covariance matrix is dependent on data structure. Interaction between first contact health provider and time will be analysed.

Secondary aim, prognostic value of number and severity of comorbidities on the course of back-related disability:

We will fit separate models for count of comorbidity (SCQ part 1, 0-15 scale) and count and severity of comorbidity (full SCQ, 0-45). The steps are outlined below:

1. The univariate association between SCQ and RMDQ over time will be assessed with a mixed model for repeated measures. An interaction term for SCQ*time will be tested, and kept if statistically significant. We will present the crude regression estimates from this analysis.
2. A mixed model with all the covariates from Table 1 and RMDQ over time will be fitted. From this model, r^2 will be presented as a measure of prognostic value.
3. SCQ will be added to the model from step 2. The adjusted regression estimate, and the r^2 -change from step 2 to step 3 will be presented.

Previous studies have found a linear relationship between number and severity of comorbidity and disability (7, 27). Linearity between SCQ and RMDQ will be assessed with a scatter-plot. In case of non-linearity between SCQ and RMDQ comorbidity count and disability score, the following alternatives will be discussed (24, 28):

- Categorization of SCQ
- Transformation (logarithmic or cubic) of SCQ
- Fractional polynomials for SCQ
- Spline functions for SCQ

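### Comorbidity and disability SAP: no planned model separates severity of comorbidity from number, because the full SCQ contains the count and the two are fitted only separately

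*Combined protocol and SAP*

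**What the plan says.** All references are to the comorbidity and disability SAP dated 22.03.2021.

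- **Study aim.** The second of the two aims reads: "to assess the prognostic value of number and severity of comorbidity at baseline for changes in back-related disability over one year of follow-up".
- **Prognostic factor measurement.** Each condition gives "1 point for the presence of a comorbidity", then "1 point if they receive treatment for the condition, and 1 point if the condition limits their functioning". The last two depend on the first: "you only answer level 2 and 3 if you have answered “yes” on level 1". The same section announces the modelling: "We plan to use SCQ part 1 comorbidity count (0-15 scale), and the full SCQ (0-45) in separate models".
- **Secondary aim, under Model choice and model building strategy.** "We will fit separate models for count of comorbidity (SCQ part 1, 0-15 scale) and count and severity of comorbidity (full SCQ, 0-45"). Step 1 gives the crude association, with an SCQ-by-time interaction kept if significant. Step 2 fits the covariates. Step 3 reads: "SCQ will be added to the model from step 2"; the adjusted estimate and the r²-change from step 2 are then reported.
- **Statistical power consideration.** With N = 450 and an r² of 0.30 for the full model, power exceeds 90% for an r²-change of 0.017 when comorbidity is added to the covariates.

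No severity-only score is defined, no model holds count and severity together, and no rule is given for comparing the two r²-changes. The only sensitivity analysis is complete case. The shell for the association table has rows for comorbidities and covariates but none for severity.

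**The concern.** The scoring makes the full SCQ (0-45) the sum of the count (0-15) and the treatment and limitation points (0-30). A condition that is present adds a point to both scores, and severity points can be scored only on conditions already counted. The two predictors are therefore correlated by construction. When each is added alone to the same covariate model, the full SCQ carries much of whatever the count predicts, whether or not severity matters.

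At stake is the severity part of the secondary aim. A significant full-SCQ coefficient or r²-change could easily be taken to mean that severity is prognostic, when it is also what one would expect if only the number of conditions mattered. The SAP classes this aim as confirmatory research on a prognostic factor, which is a reason to specify the contrast in advance.

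**Working it through.** **Inputs from the SAP.** N = 450; full-model r² = 0.30; r²-change 0.017; two-sided α = 0.05; full SCQ = count (0-15) + severity points (0-30).

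**Assumed.** ρ, the correlation of count and full SCQ given the covariates, is not in the documents; I use 0.70 to 0.95. Simple simulations (mean 1.5 to 2.5 conditions, 40-60% treated, 20-40% limiting, with and without variation in severity between patients) gave 0.88 to 0.94. Stronger variation between patients lowers it, to about 0.81 in one set of assumptions.

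**1. The plan's own power figure.** For one added predictor, λ = N × Δr² / (1 − r²), referred to a noncentral F with 1 and N − k − 1 degrees of freedom.

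λ = 450 × 0.017 / 0.70 = 10.93, so power = 91.0%, unchanged to one decimal for k = 7 to 15. If 0.30 is instead the r² before comorbidity is added, power is 91.6%. The stated figure reproduces.

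**2. What the full SCQ shows when severity adds nothing.** If the outcome depends on comorbidity only through the count, then

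Δr²(full SCQ) = ρ² × Δr²(count).

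With Δr²(count) = 0.017, the r² of the full-SCQ model is 0.283 + Δr²(full SCQ), because 0.30 − 0.017 = 0.283.

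| ρ (assumed) | Δr² of full SCQ | λ | Chance of p < 0.05, N = 450 |
|---|---|---|---|
| 0.70 | 0.49 × 0.017 = 0.0083 | 5.3 | 63% |
| 0.80 | 0.64 × 0.017 = 0.0109 | 6.9 | 75% |
| 0.90 | 0.81 × 0.017 = 0.0138 | 8.8 | 84% |
| 0.95 | 0.9025 × 0.017 = 0.0153 | 9.8 | 88% |

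**3. Check by simulation.** I used 4,000 cohorts of 450 per scenario with ordinary regression, a mean of 2 conditions, on average 50% treated and 30% limiting, and ρ about 0.90.

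- No severity effect: the full-SCQ model was significant in 84% of cohorts. Severity given count, in a joint model, was significant in 4.7%, close to the nominal 5%.
- Same scenario, comparing the two r² values by eye: the full SCQ exceeded the count in 22.5% of cohorts by chance.
- A severity point with half the effect of a count point: the full SCQ exceeded the count in only 65%.

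**4. Power of a joint model.** The step from covariates + count to covariates + count + severity again adds one predictor, so the formula in step 1 applies with Δr² now that of severity given count. The documents give no expected value; these are assumed.

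| Δr² of severity given count | λ = 450 × Δr² / 0.70 | Power, N = 450 |
|---|---|---|
| 0.002 | 1.29 | 20.5% |
| 0.005 | 3.21 | 43% |
| 0.010 | 6.43 | 72% |
| 0.017 | 10.93 | 91% |

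Steps 1 to 4 treat the outcome as a single measurement, as the SAP's own power statement appears to. The planned mixed model uses repeated visits, so the percentages are a guide to size. The overlap between the two scores does not depend on this simplification.

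**The case against.** The strongest reply is that the plan does what it says. The aim names number and severity; it does not say severity beyond, or independent of, number. The SAP itself labels the full SCQ as count and severity together, and the table shell promises no severity result. Read literally, the plan evaluates two alternative scores against one covariate model. This stands: a reader might infer that the SAP fails its own aim, but the text does not state an incremental question.

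A reader might also infer that the two models cannot be compared. That is too strong. They share the outcome, the patients and the step 2 model, and non-nested models can be compared by AIC, a Vuong-type test or a bootstrap of the r² difference. In the population, a larger r²-change for the full SCQ would imply that severity adds something. What stands is that the SAP specifies no such comparison and that an informal one is unreliable, as the 22.5% and 65% above show.

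A third tempting reading is that the scores are almost interchangeable, with a correlation near 0.95. No figure in the documents fixes it there, and moderate variation in severity between patients lowers it. Nor is the stated power wrong: it reproduces, but it concerns comorbidity added to covariates.

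Finally, the SAP presents its model building as a framework that leaves room for choices, so a joint model would be allowed. But the alternatives it lists for the SCQ deal only with non-linearity, and exploratory post hoc analyses must be labelled as such.

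**Conclusion.** The point holds in a limited form. No planned estimate separates severity from number, and a significant full-SCQ result is not evidence that severity is prognostic. With the plan's own inputs and no severity effect at all, such a result would still arise about 63% to 88% of the time across an assumed ρ of 0.70 to 0.95. That range rests on ρ, on a count r²-change of 0.017 and on the single-measurement approximation; the containment of one score in the other follows directly from the scoring rules.

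The documents do not show that the authors intend to read the full-SCQ estimate as severity alone. The gap matters if any conclusion about severity itself is to be drawn. It is a worthwhile and inexpensive improvement rather than a flaw that invalidates the two planned models.

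**What to change.** Add a step 4 to the secondary-aim analysis: one mixed model with the count and the severity points (full SCQ minus count, 0-30) together, with the same covariates, and with the time interaction for both terms if it is kept. Report the severity coefficient with its 95% confidence interval and the r²-change of severity given count, and base every statement about severity on this model. Say that the power statement does not cover this step and that a non-significant result is to be read from the interval, not as proof of no effect.

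If the authors prefer not to add it, one sentence should state that the aim is to compare two alternative scores, name the comparison to be used, and rule out conclusions about severity on its own.

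The cost is one extra model on baseline items already in the questionnaire, one table row and a short addition to the SAP. The drawback is that the severity estimate may be imprecise. If the analysis has already been run, the model can still be added, labelled post hoc.

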Patients aged ≥ 55 years visiting a general practitioner (GP), physiotherapist or chiropractor for a new episode of back pain are invited to participate in the study. Back pain is defined as pain located in the region from the top of the scapula to the sacrum, with or without radiating leg pain. An episode of back pain is defined as “new” if the patient has not received health care for the same back complaint during the last 6 months. The exclusion criteria were: Difficulty completing the study questionnaires due to language or cognitive difficulties, mobility impairments impeding the clinical examination (wheelchair-bound patients), had received healthcare for the same back complaint during the last 6 months (notwithstanding care initiated within the previous 4 weeks from time of baseline assessment).

Data collection

At baseline, patients receive a clinical examination and questionnaire. Patients are then given a follow-up questionnaire either through email or mail at 3-months, 6-months and 12-months follow-up.

Description of treatment received during follow-up

The study participants continue their health care in agreement with their healthcare provider regardless of inclusion in the study. This means that patients may receive education and advice, exercise therapy, massage, manipulations, mobilizations, pharmacological therapy, or additional diagnostic testing and referrals, all of which constitutes “usual” primary care (15). Treatment given is at the discretion of the healthcare provider and the patient.

Variables

Outcome measure:

Back-related disability, measured using the Norwegian, validated version of the Roland-Morris Disability Questionnaire (RMDQ) (16, 17). This is a questionnaire with 24 statements regarding abilities to perform ADL tasks, with a dichotomous yes/no answer. The answers are summed to a total score ranging from 0-24, where 0 indicates no disability and 24 indicates “maximum” disability. RMDQ has been found to measure several dimensions of back-related disability (18). We plan to use RMDQ as a continuous measure, as recommended by the PROGRESS framework (14). This will ensure easier comparability to similar studies, and easier inclusion in future meta-analyses.

RMDQ is measured at baseline, 3 months, 6 months and 12 months.

Prognostic factor measurement:

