Back pain duration	Measured in days, but categorized to an ordinal scale of 3 categories: 0-6 weeks, 6-12 weeks, >12 weeks, similar to other BACE studies (22)	Covariate in previous study (8), and found to be associated with disability in older adults (4, 6, 11, 20)
Baseline disability	Continuous. Roland-Morris disability questionnaire, 0-24 scale.	Standard covariate, given the outcome is disability. Only applicable if not using mixed models.
Pain severity last week	Continuous. Numeric rating scale 0-10.	Associated with disability in one study in older adults (4).
Expectation of recovery within the next three months	5-point ordinal Likert scale. From “I am fully recovered” to “I am worse than ever”.	Consistently associated with disability in older adults (4, 6, 11)

Statistical power consideration

The published protocol for the BACE-N study estimates that we need a total of 450 patients included in the study. Allowing a 15% dropout rate at 12 months, we will have approximately 380 participants available at 12 months.

We used the power estimation tool in Stata to determine level of statistical power. With a sample size of 450, and an estimated r^2 of 0.30 for the full model of comorbidity adjusted for covariates, we have over 90% power to detect an r^2 -change of 0.017 or higher when adding comorbidity to the model.

Handling of missing data

Missing data will be handled with multiple imputation, using 5 imputations and 10 iterations unless the missing exceeds 30% and missing at random cannot be assumed. We will use the fully conditioned specification method, and regression estimation. For variables where we are unable to use regression estimation due to computational difficulties, predictive mean matching will be used (23).

Missing values for RMDQ will be handled by replacing missing items with the mean of the answered items for the individual, if less than 30% of the items are missing.

A mixed model, which we intend to use for the primary and secondary aim, does not require variable level imputation for the outcome measure. However, missing values on item level on

the RMDQ might still be an issue. To solve this, we will replace missing items for RMDQ with the mean of the answered items for the individual, if less than 7 (30%) of the 24 items are missing.

Statistical analyses

General statistical considerations

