Analyses described in this statistical analysis plan are considered a priori analyses. Possible post-hoc exploratory analyses will be explicitly identified in the article. All analyses will be carried out by the first author using Stata version 16, under supervision from the principal investigator and the advisory statistician. The statistical tests will be 2-sided, and p-value will be reported. If the p-value is less than 0.05, the test is deemed statistically significant. 95% confidence intervals will be reported on point estimates.

Statistical analyses

Description of study flow and study sample:

The flow of participants will be reported with a flow chart. Reasons for exclusion and loss to follow-up will be provided where known. Descriptive data of the study sample will be reported using mean and standard deviation for normally distributed continuous variables, median and interquartile range for variables with skewed distribution, and with frequency and proportions for categorical variables. Normal distribution will be examined visually using histogram and QQ-plot, and statistically with the Kolmogorov-Smirnov test. Baseline characteristics will be presented in a table. See proposed tables and figures below.

Descriptive statistics will be used to present the mean and standard deviation if RMDQ is normally distributed, or median and interquartile range if RMDQ is not normally distributed, for each time point: Baseline, 3 months, 6 months, 12 months. This will also be presented graphically, similarly to van der Gaag et al (3). This graphical presentation will also be performed stratified for number of comorbidities.

A person may be a responder at one time-point and a non-responder at another. Therefore, an analysis of responders versus non-responders will be performed for each time point, using bivariate analysis for baseline characteristics (chi square test, Individual Samples T-test, or Mann Whitney U-test). Results from these analyses will be presented in text, and the table available in supplementary material.

Model choice and model building strategy:

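### The comorbidity SAP aims at change in disability, but the only term that measures change is kept only if significant and is not named in the adjusted model

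*Combined protocol and SAP*

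**What the plan says.** All references are to the SAP on clinical course and comorbidity dated 22.03.2021.

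- **Study aim.** The second of the two aims reads: "to assess the prognostic value of number and severity of comorbidity at baseline for changes in back-related disability over one year of follow-up".
- **Outcome measure.** "RMDQ is measured at baseline, 3 months, 6 months and 12 months". The missing-data section says a mixed model is intended for both aims.
- **Table 1, baseline disability row.** "Standard covariate, given the outcome is disability. Only applicable if not using mixed models". Under the intended model, baseline RMDQ is therefore not a covariate.
- **Secondary aim, step 1 (crude).** "An interaction term for SCQ*time will be tested, and kept if statistically significant".
- **Step 2.** "A mixed model with all the covariates from Table 1 and RMDQ over time will be fitted".
- **Step 3.** "SCQ will be added to the model from step 2". One adjusted estimate and the r-squared change from step 2 are then presented. The interaction is not mentioned.
- **Draft results table.** There are three rows (comorbidities, covariates, comorbidities with covariates) and columns for beta, CI and R². There is no SCQ-by-time row.
- **Primary aim, for contrast.** "Interaction between first contact health provider and time will be analysed", with no significance condition.

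**The concern.** Leaving baseline RMDQ out of the covariates is not an error when baseline is one of the outcome rows. It does mean that the SCQ main effect is not conditioned on entry disability, so the whole question about change rests on SCQ-by-time. If that term is absent, the model imposes the same SCQ difference at every visit, entry included, and both the coefficient and the r-squared change describe level.

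Two errors follow. A comorbidity difference already present at entry can be reported as prognostic value for change. A real but modest difference in change can be removed by the significance filter, leaving a diluted average in its place. The plan prespecifies no adjusted estimate of differential change anywhere.

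A separate inconsistency affects the same table. Step 2 uses the Table 1 covariates. The table's footnote instead lists education, smoking, alcohol and probable radicular pain, leaves recruiting profession undecided, and omits BMI, pain severity and recovery expectation.

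**Working it through.** **Inputs from the SAP:** N = 450; 15% dropout at 12 months (about 380 left); full-model r² = 0.30; r² change 0.017; two-sided alpha 0.05; four visits.

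**Assumed:** within-person correlation ρ = 0.4 to 0.7, equal between all pairs of visits; RMDQ variance 1 per visit; categorical time.

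**1. The plan's own power figure.** f² = 0.017/(1 − 0.30) = 0.0243 and λ = 450 × 0.0243 = 10.9. The 1-df noncentral F gives 91.0%, so the stated power of over 90% reproduces. It is power for adding SCQ, not SCQ-by-time. If a 3-df interaction explained the same 0.017, the same formula gives 79.7–80.8% at N = 450 (full-model r² 0.30 or 0.317).

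**2. What the single coefficient measures.** With four balanced visits and equal correlations, the SCQ coefficient without an interaction is the plain mean of the four visit-specific differences. Assumed effects in RMDQ points per SCQ point:

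| Baseline | Each follow-up | Single coefficient | True change |
|---|---|---|---|
| 0.5 | 0.5 | 0.50 | 0 |
| 0 | 0.5 | 0.375 | 0.5 |
| −0.3 | 0.1 | 0 | 0.4 |

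**3. Parallel courses at the planning values.** SCQ has a level association worth r² 0.017 and no effect on change. On subject means, the residual variance is (1 + 3ρ)/4 − 0.30, f² = 0.017 divided by that, and λ = 450 f². Simulated values are from 2,000 cohorts per setting (random-intercept REML; dropout 5/10/15% at 3/6/12 months).

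| ρ | Residual variance | λ | Step 3 significant, formula | Step 3 significant, simulated | SCQ-by-time significant | Interaction dropped and step 3 significant |
|---|---|---|---|---|---|---|
| 0.4 | 0.250 | 30.6 | 100% | 100% | 5.1% | 94.9% |
| 0.5 | 0.325 | 23.5 | 99.8% | 99.4% | 4.4% | 95.2% |
| 0.6 | 0.400 | 19.1 | 99.2% | 98.9% | 5.0% | 94.0% |
| 0.7 | 0.475 | 16.1 | 98.0% | 97.6% | 4.4% | 93.3% |

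A weaker case has two covariates correlated 0.5 and 0.4 with RMDQ and 0.15 with SCQ (all assumed), at ρ = 0.4 to 0.7. Step 3 is then significant in 30–50% at an SCQ–RMDQ correlation of 0.15, and in 87–99% at 0.20.

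**4. A real effect on change.** SCQ is unrelated to baseline RMDQ, and a difference of 0.10 SD per SD of SCQ is present from 3 months on. For the 3-df test with complete data, λ = 450 × 0.10² × 0.75/(1 − ρ).

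| ρ | λ | Dropped, formula | Dropped, simulated with dropout |
|---|---|---|---|
| 0.4 | 5.6 | 51% | 53% |
| 0.55 | 7.5 | 38% | 40% |
| 0.7 | 11.25 | 19% | 22% |

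When the term is dropped, the single coefficient averages about 0.07 instead of 0.10.

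**5. Why covariate main effects are not enough.** With balanced data, the SCQ-by-time contrasts are identical with and without a covariate's main effect. Simulation: a covariate predicts change (−0.2 to −0.3 SD per SD; correlation with SCQ 0.15 to 0.30, assumed) and SCQ has no effect on change. SCQ-by-time is then significant in 8–66% with the covariate's main effect only, and in 4–6% once covariate-by-time is included.

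**6. Baseline-adjusted alternative.** Under the parallel courses of step 3, a follow-up-only model adjusted for baseline RMDQ rejects in 98.6/91.4/76.0/58.4% at ρ = 0.4/0.5/0.6/0.7. It is not a test of change either.

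**The case against.** The SAP calls its modelling section a framework, so the authors could carry a retained interaction into step 3. It also says that p-values will be reported, so a non-significant SCQ-by-time result need not be hidden. Of the graph of the course, it says: "This graphical presentation will also be performed stratified for number of comorbidities"; a draft table also gives unadjusted RMDQ at each visit by comorbidity count. An entry gap with parallel courses would be visible there. The word for change appears only in the aim. The title, power statement and results table fit an association with disability over the year, so rewording the aim would also remove the mismatch. The 98–100% is power for a level association that was built in, and the other scenarios rest on assumed values.

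Part of this stands. Step 3 is silent rather than explicit, so the estimate *can* be level only; it need not be. The 98–100% becomes an error only when the result is read as an answer about change, but the stated aim asks for that reading. A p-value, a graph and an unadjusted table do not supply an adjusted estimate of differential change with a CI. With a real difference missed in 22–53%, a non-significant interaction does not establish parallel courses. Rewording the aim would make the document consistent by giving up the question about change.

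**Conclusion.** The concern holds. Followed as written, steps 1 to 3 can answer an aim about change with an average level difference that includes entry. At the SAP's own r² values with parallel courses, the interaction is dropped and the adjusted SCQ estimate is significant in 93–95% of simulated cohorts. A true 0.10 SD difference in change is filtered out in 22–53%. These figures rest on an assumed within-person correlation of 0.4 to 0.7, categorical time and the stated dropout pattern, and the second also on an assumed effect size. That the single coefficient does not measure change follows from the model alone. The stated power is correct for what it tests, but it does not cover the interaction. This should be fixed before the secondary analysis is run or reported.

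**What to change.** 1. Keep all four visits as outcome rows. Retain SCQ-by-time in the crude model and in the adjusted step 3 model whatever its p-value, and add it to the results table.
2. Report the SCQ difference in change from baseline at 3, 6 and 12 months with 95% CIs as the answer to the secondary aim. Label the SCQ main effect a level association, and attribute to prognosis for change only the r-squared gained from SCQ-by-time.
3. Give the Table 1 covariates time interactions in the adjusted model. Main effects alone leave the SCQ-by-time contrasts essentially unadjusted.
4. A follow-up-only model adjusted for baseline RMDQ may be added, labelled as prognostic value beyond entry disability and not as a test of change.
5. Make the results-table footnotes match the Table 1 covariates that step 2 names.
6. State that the power figure is for the 1-df addition of SCQ and does not apply to the interaction.

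**Cost.** The data and software are unchanged. The SAP wording changes, and the results table grows by three contrasts, crude and adjusted, for each of the two SCQ versions. The change estimates will be less precise and probably smaller than the single level coefficient, and the covariate-by-time terms use more parameters. The r-squared for change will also be small: in the 0.10 SD scenario it is about 0.10² × 0.75 × 0.25 = 0.002, against chance gains of 0.0005–0.0011 under parallel courses. The contrasts with their CIs should therefore carry the conclusion.
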